## 16.1.4. Supplementary Analysis of Primary Efficacy Variable(s)

A repeated measure mixed model (MMRM) will be performed on the primary efficacy endpoint to test the covariate effects and the effects of interactions between the covariates for the only mITT population. The MIXED model will include change in mean sitting SBP as the dependent variable, repeated through visits Visit 3 (Week 4), Visit 4 (Week 8) and Visit 5 (Week 12). Age (years), gender, body mass index (BMI), and baseline SBP are considered as the covariates. The MIXED model is

SBP Change from Baseline = Visit + Age + Gender + BMI + baseline SBP + Age\*Gender + Age\*BMI + Age\*baseline SBP + Gender\*BMI + Gender\*baseline SBP + BMI\*baseline SBP + Age\*Gender\*BMI + Age\*Gender\*baseline SBP + Age\*BMI\*baseline SBP + Gender\*BMI\*baseline SBP + Age\*Gender\*BMI\*baseline SBP + Age\*Gender\*BMI\*baseline SBP

A PROC MIXED procedure, with an unstructured covariance matrix, is used for the analysis and the corresponding two-sided p-values for each of the covariates will be presented in a table. If the fit of the unstructured covariance structure fails to converge, the following covariance structures will be tried in order until convergence is reached: Toeplitz with heterogeneity, compound symmetry, autoregressive with heterogeneity, toeplitz, and autoregressive. Smaller value of AIC and BIC will be considered for selection of best fit for covariance structure.

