#### 6.2. Baseline

Unless otherwise specified, baseline is defined as the last non-missing measurement taken same day or prior to reference start date (including unscheduled assessments) before first dose of study medication (monotherapy or combination therapy. Adverse Events (AEs) and medications commencing on the reference start date/time will be considered post-baseline, unless the start time of the AE is known to be prior to the first dosing of the study drug. Since there is no Lab assessment in Visit 2, Lab values collected at Visit 1 will be considered baseline for Lab data. For combination therapy related analysis, the baseline will be the measurements that are taken at Visit 2 (Week 0).

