#### 6.6. Common Calculations

For quantitative measurements, change from baseline will be calculated as:

• Test Value at Visit X – Baseline Value

And for change between Visit 3 and Visit 4 will be calculated as:

• Test Value at Visit 4 – Visit 3 Value

And for change between Visit 4 and Visit 5 will be calculated as:

• Test Value at Visit 5– Visit 4 Value

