# 16.2.1.3. CHANGE IN MEAN SITTING DBP BETWEEN VISIT 2 (WEEK 0) AND VISIT 5 (WEEK 12)

Change from baseline in sitting DBP from prior and post combination therapy will be compared using paired t-test. The p-value will be presented using a paired t-test comparing mean at baseline and mean at Week 12. The secondary endpoint will be presented in a descriptive manner using n, mean, median, SD, Q1, Q3, and minimum and maximum. Assumption of normality will be investigated using Wilk-Shapiro test. If violation is observed, then paired t-test will be replaced by Wilcoxon signed rank test.

Additionally, the secondary end point of change in DBP between Visit 2 and Visit 5 will be analyzed using a repeated measures mixed model MMRM as described in Section 16.1.4 with Age (years), Gender, body mass index, and baseline DBP as covariates to identify the effect of covariates and interaction between the covariates.

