## **Reference Code**

Paired t-test

```
ods trace on;

proc ttest data=input_data h0=0;

paired VISITX*VISITY;

ods output TTests=test;

run;

ods trace off;
```

Normality assumption check

```
ods trace on;

proc univariate data=indata normal plot;

var change from baseline;

histogram /normal kernel(color=red);

ods output TestsForNormality=norm(where=(test="Shapiro-Wilk"));

run;

ods trace off;
```

Wilcoxon Signed Rank Test

Page 43 of 46

Statistical Analysis Plan v 3.0

run;

```
ods trace on;
proc univariate data=indata mu0=0 loccount;
  var change from baseline;
  ODS Output TestsForLocation=test LocationCounts=LOCC one;
       Exact McNemars Test
ods trace on;
ods output McNemarsTest=McNemarsTest;
proc freq data=indata order=data;
  tables VISITX*VISITY/agree alpha=0.05;
  exact mcnem;
  weight ZZZ/zeros;
run;
       Independent sample t-test
ods trace on:
proc ttest data=indata h0=0;
class xxx;
var change from baseline;
run;
ods trace off:

    Wicoxon Rank Sum Test

ods trace on;
proc npar1way data=indata wilcoxon;
  by by variables;
  class xxx;
  var change from baseline;
  ods output WilcoxonTest=wt;
run:
       Repeated measures Mixed Model
proc mixed data=indata;
class visit sex;
model change from baseline = Visit Age Gender BMI baseline SBP Age*Gender
Age*BMI Age*baseline SBP Gender*BMI Gender*baseline SBP BMI*baseline SBP
Age*Gender*BMI Age*Gender*baseline SBP Age*BMI*baseline SBP Gender*BMI*baseline SBP
Age*Gender*BMI*baseline SBP;
repeated visit;
```

**■IQVIA**™

Imputed dates will NOT be presented in the listings.

Algorithm for Treatment Emergence of Adverse Events:

START DATE	STOP DATE	ACTION
Known	Known/Partial/	If start date < study med start date, then not
	Missing	TEAE
		If start date >= study med start date, then TEAE
Partial, but known	Known/Partial/	Not TEAE
components show that it	Missing	
cannot be on or after		
study med start date		
Partial, could be on or	Known	If stop date < study med start date, then not
after study med start		TEAE
date		If stop date >= study med start date, then TEAE
OR Missing		
	Partial	Impute stop date as latest possible date (i.e. last
		day of month if day unknown or 31st December if
		day and month are unknown), then:
		If stop date < study med start date, then not
		TEAE
		If stop date >= study med start date, then TEAE
	Missing	Assumed TEAE

Page 45 of 46

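### SAP 16.1.4 tests Visit 2 blood pressure as a predictor of change from Visit 2, so the baseline slope includes regression to the mean and cannot show effect modification

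*SAP*

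**What the plan says.** SAP 16.1.4 adds a repeated-measures mixed model to the primary paired t-test. "The MIXED model will include change in mean sitting SBP as the dependent variable", repeated over Visits 3, 4 and 5. "Age (years), gender, body mass index (BMI), and baseline SBP are considered as the covariates". The model crosses these four covariates up to the four-way product, and the Reference Code in Appendix 1 does the same. No centring is stated, and the model has no treatment term.

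The aim is to test, not only to adjust. The model is run "to test the covariate effects and the effects of interactions between the covariates", and "the corresponding two-sided p-values for each of the covariates will be presented in a table".

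SAP 6.6 defines change from baseline as "Test Value at Visit X – Baseline Value", and SAP 6.2 takes the Visit 2 (Week 0) measurement as baseline for combination-therapy analyses.

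SAP 16.2.1.1 to 16.2.1.3 carry the approach to secondary BP changes. For DBP at Week 12 it is age, gender, BMI and "baseline DBP as covariates to identify the effect of" covariates and their interactions.

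Protocol 12.1 has every patient receive the combination, without randomisation. Protocol 5 lets only patients uncontrolled at Visit 2 continue. Neither document mentions regression to the mean or says how a baseline effect should be read.

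**The concern.** Any chance departure of the Visit 2 value from a patient's usual level enters the outcome with a minus sign and the covariate with a plus sign. A patient who happens to read high at Visit 2 tends to show a larger later fall whatever the drug does. The departure includes visit-to-visit biological variation as well as reading error, so averaging three readings within a visit does not remove it.

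In a randomised comparison the baseline term is a nuisance adjustment and this does no harm. Here there is one group, and the covariate effects are themselves the reported output. At stake is a conclusion that patients with higher starting BP respond more to the combination. That is clinically attractive, but this model cannot separate it from regression to the mean.

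**Working it through.** **Inputs from the documents.** N = 215 completers and SD 12.0 mmHg (protocol 12.2); outcome, covariates and interactions (SAP 16.1.4, Appendix 1); baseline and change (SAP 6.2, 6.6).

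**Assumptions.** The 12 mmHg is taken as the SD of the single-visit change. Within-visit SD is varied from 2 to 8.4 mmHg because the documents give none. Mean fall is unrelated to BP level.

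**The plan's own figure.** No size is stated for the mixed model. The sample size reproduces: (12 × (1.645 + 1.282) / 2.4)² = 214.1, rounded up to 215.

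**Slope under a uniform effect.** Let T be the usual level, Visit 2 reading X = T + e₂, and later reading Y = T - δ + e. Then Y - X = -δ + e - e₂, and its covariance with X is -var(e₂). So

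slope = -var(e) / (var(T) + var(e)) = -(1 - R), where R is the reliability.

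If within-person variation accounts for the whole SD of change, its SD is 12/√2 = 8.49. With one post-baseline visit, r = -√((1 - R)/2) and t = r√213/√(1 - r²):

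| R | slope | r | t at n = 215 |
|---|---|---|---|
| 0.5 | -0.50 | -0.50 | -8.4 |
| 0.7 | -0.30 | -0.39 | -6.1 |
| 0.8 | -0.20 | -0.32 | -4.9 |
| 0.9 | -0.10 | -0.22 | -3.4 |

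Selection on Visit 2 narrows the baseline range but leaves the slope unchanged (-0.499 with selection, -0.498 without, at R = 0.5).

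**Smaller within-visit SD.** Hold the true SD at 8.49 (variance 72), its value at R = 0.5. The rest of the 12 mmHg must then come from differences in response unrelated to baseline, which dilute the test. The slopes are:
- SD 2: -4/76 = -0.05
- SD 4: -16/88 = -0.18
- SD 6: -36/108 = -0.33
- SD 8.4: -70.6/142.6 = -0.50

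**Simulated rejection of no baseline effect at 5%.** Settings: n = 215, Visit 1 and Visit 2 entry rules applied to SBP, SD of change 12. Also assumed, for example: true SBP before selection mean 148 and SD 12, age 58 (SD 12), BMI 29 (SD 4.5). Ranges cover separate runs with somewhat different settings.

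| Within-visit SD | Additive model | Full factorial, centred | Full factorial as written |
|---|---|---|---|
| 2 | 8-10% | 8% | 4-7% |
| 4 | 50-60% | 45-56% | 4-7% |
| 6 | 98-99.8% | 98-99% | 4-7% |
| 8.4 | 100% | 100% | 4-7% |

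**Why the last column is flat.** With uncentred products in the model, the single line for baseline SBP is its slope at age 0 and BMI 0, far outside an adult sample and very imprecisely estimated. The artefact is still in the fit. A joint test of all terms containing baseline SBP, which the SAP does not specify, rejects in about 6% of trials at SD 2, rising to 100% at SD 8.4.

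**Interactions.** With equal within-visit variation in all patients, the products of baseline SBP with age, sex and BMI reject in 3.8-6.7%. Age by baseline rose to 13% when variation was made to grow with age.

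**Visit 1 SBP instead.** In an additive model its slope is 0.01 to 0.06 and it rejects in 4-13.5%, highest at SD 8.4. The residual arises because a patient with a low Visit 1 value needs a chance-high Visit 2 value to continue. In the factorial as written, the swap leaves rejection at 4-6%, as before.

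**Limit of the check.** Covariate effects were tested on each patient's mean change. That matches the mixed model under compound symmetry with complete data; an unstructured covariance was not fitted.

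**The case against.** Baseline as a covariate in a change-score model is ordinary ANCOVA with the coefficient shifted by -1. The analysis is labelled supplementary, and the SAP nowhere says that it will claim a larger response in patients with higher BP. In the model as specified, the tabulated baseline p-value does not show the artefact. The size depends on a within-visit SD that the documents do not give, and each value is already a mean of three readings.

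All of this stands and limits the point. It does not answer it: the SAP's stated purpose is to test covariate effects, and the baseline line of the table cannot do so. As written it describes a patient of age 0 and BMI 0. Centring or dropping interactions, the natural repairs, would expose the artefact.

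A reader might infer three stronger things that the documents do not support:
- **That the report will show a highly significant baseline effect whatever the truth.** That follows for an additive or centred model with enough within-visit variation, not for the four-way model in SAP 16.1.4.
- **That the baseline interactions carry the same artefact.** They do so only if reliability differs by age, sex or BMI, on which the documents say nothing.
- **That replacing Visit 2 by Visit 1 SBP in the specified model cures it.** It changes nothing there.

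**Conclusion.** The concern holds as one of interpretation. SAP 16.1.4, and 16.2.1.1 to 16.2.1.3 after it, test baseline BP against change from the same baseline, with no control arm to separate regression to the mean from a real dependence on starting BP. Under a uniform drug effect the built-in slope is about -0.05 to -0.5 for an assumed within-visit SD of 2 to 8.4 mmHg. Whether it reaches significance depends on that SD and on the model's form, and the p-value specified now is uninterpretable in any case. The primary paired t-test uses no covariate and is unaffected by this coefficient.

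**What to change.** In SAP 16.1.4 and 16.2.1.1 to 16.2.1.3:
- keep Visit 2 BP as an adjustment term only, with no p-value and no interactions;
- centre the continuous covariates;
- state that the baseline slope includes regression to the mean and will not be read as effect modification.

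If an effect of severity is wanted, test Visit 1 BP in that simplified, centred model.

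The cost is SAP wording and the matching table shells, which SAP 4 ties to a SAP amendment. No new data are needed, since Visit 1 BP is already collected. The downsides are that the baseline interaction tests are lost, the Visit 1 test still rejects in about 10-13% of trials when within-visit variability is high, and Visit 1 BP precedes the therapy switch in some patients.

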## 7.1. Adjustments for Covariates and Factors to be Included in Analyses

The following covariates and factors are used in the analyses.

- Treatment
- Age (eCRF page: Demography)
- Gender (eCRF page: Demography)
- Body Mass Index (eCRF page: Physical Examination)
- Baseline SBP
- For details of their inclusion in the models, see the specific analysis section

Page 21 of 46

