# 16.2.1.1. CHANGE IN MEAN SITTING SBP AND DBP BETWEEN VISIT 2 (WEEK 0) AND VISIT 3 (Week 4)

Change from baseline in sitting SBP and DBP from prior and post combination therapy will be compared using paired t-test. The p-value will be presented using a paired t-test comparing mean at baseline and mean at Week 4. The secondary endpoint will be presented in a descriptive manner using n, mean, median, SD, Q1, Q3, and minimum and maximum. Assumption of normality will be investigated using Wilk-Shapiro test. If violation is observed, then paired t-test will be replaced by Wilcoxon signed rank test.

Additionally, the secondary end point of change in SBP and DBP between Visit 2 and Visit 3 will be analyzed using a repeated measures mixed model MMRM as described in Section Error! Reference source not found. with Age (Years), Gender, body mass index, and baseline BP (SBP or DBP) as covariates to identify the effect of covariates and interaction between the covariates.

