# 16.2.1.2. CHANGE IN MEAN SITTING SBP AND DBP BETWEEN VISIT 2 (WEEK 0) AND VISIT 4 (Week 8)

Change from baseline in sitting SBP and DBP from prior and post combination therapy will be compared using paired t-test. The p-value will be presented using a paired t-test comparing mean at baseline and mean at Week 8. The secondary endpoint will be presented in a descriptive manner using n, mean, median, SD, Q1, Q3, and minimum and maximum. Assumption of normality will be investigated using Wilk-Shapiro test. If violation is observed, then paired t-test will be replaced by Wilcoxon signed rank test.

Additionally, the secondary end point of change in SBP between Visit 2 and Visit 4 will be analyzed using a repeated measures mixed model MMRM as described in Section Error! **Reference source not found.** with Age (Years), Gender, body mass index, and baseline BP (SBP or DBP) as covariates to identify the effect of covariates and interaction between the covariates.

Page 30 of 46

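### The covariate MMRM in SAP 16.1.4 states neither centring nor a test type; with partial (Type 3) tests on uncentred covariates, most of its main-effect and interaction p-values would be uninformative (minor, supplementary tables only)

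*SAP*

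**What the plan says.** SAP 16.1.4 adds a repeated-measures mixed model to the primary analysis. Its purpose is "to test the covariate effects and the effects of interactions between the covariates". The response is change in SBP at Weeks 4, 8 and 12. "Age (years), gender, body mass index (BMI), and baseline SBP are considered as the covariates", and the model holds visit, the four main effects, all six two-way products, all four three-way products and the four-way product (printed twice). The output is described as "the corresponding two-sided p-values for each of the covariates will be presented in a table".

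SAP 7.1 lists the covariates and leaves the rest to the analysis section: "For details of their inclusion in the models, see the specific analysis section". Section 16.1.4 gives age in years and sets an unstructured covariance, but mentions neither centring nor the type of test. The template code in SAP Appendix 1 shows the same terms, with no centring step and no test-type option.

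SAP 16.2.1.3 reuses the model for DBP at Week 12, calling for a "repeated measures mixed model MMRM as described in Section 16.1.4". Baseline DBP takes the place of baseline SBP there; the other three covariates stay the same. Sections 16.2.1.1 and 16.2.1.2 appear to reuse it too, with "baseline BP (SBP or DBP) as covariates to identify the effect of covariates", but their cross-references print as "Reference source not found".

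**The concern.** In a model with products, a partial test of a lower-order term is a test at the point where the covariates multiplying it equal zero. No patient is near that point: protocol 6.2.1 requires age of at least 18 and raised blood pressure at screening, and a BMI or blood pressure of 0 is impossible. The test therefore extrapolates far outside the data and its standard error becomes very large.

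At stake is the one purpose of these tables, which is to show whether age, gender, BMI and baseline BP, or combinations of them, relate to the BP change. A table with almost no power invites readers to take non-significant rows as a finding.

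**Working it through.** **Inputs.** From the documents: n = 215 and SD of change 12.0 mmHg (protocol 12.2), and two-sided 5% tests (SAP 6.5). Assumed, because the documents give no figures: age 60 (SD 11), BMI 29 (SD 4.5), baseline SBP 146 (SD 9), between-visit correlation 0.6, and no true interactions unless stated.

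**The plan's own figure.** The sample size reproduces for the primary test: (12 × (1.645 + 1.282) / 2.4)² = 214.2, rounded up to 215. The plan gives no figure for the MMRM.

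**What is tested.** Averaged over gender, the age slope at given BMI and SBP is

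b(Age) + b(Age·BMI) × BMI + b(Age·SBP) × SBP + b(Age·BMI·SBP) × BMI × SBP.

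The partial test of Age is a test of b(Age) alone, so it is the slope at BMI 0 and SBP 0. BMI is likewise tested at age 0 and SBP 0, and SBP at age 0 and BMI 0. Gender is the only term tested with all three at 0. Age×Gender is tested at BMI 0 and SBP 0, and Age×SBP at BMI 0. Only Age×BMI×SBP (with gender effect-coded) and the four-way term have no further continuous covariate multiplying them.

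**Size of the standard-error inflation.** For independent covariates in large samples, the ratio of uncentred to centred standard error is the square root of the product of (1 + (mean/SD)²) over the covariates held at zero. The factors are:
- age: 1 + (60/11)² = 30.75
- BMI: 1 + (29/4.5)² = 42.53
- SBP: 1 + (146/9)² = 264.16

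The ratios are then:
- age slope, and Age×Gender: √(42.53 × 264.16) = 106
- SBP slope: √(30.75 × 42.53) = 36
- gender: √(30.75 × 42.53 × 264.16) = 588
- Age×SBP: √42.53 = 6.5

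Simulated median standard errors at n = 215 are somewhat worse: 8.33 against 0.068 for age (ratio 122) and 3.46 against 0.083 for SBP (ratio 42). An age slope of −0.2 per year is thus 0.2/8.33 = 0.02 standard errors uncentred and 0.2/0.068 = 2.9 centred.

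**Detection, 4,000 simulated trials.**

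| Assumed true effect | Uncentred, partial | Centred, partial | Uncentred, sequential | No interactions fitted |
|---|---|---|---|---|
| SBP slope −0.4 | 5.4% | 99.7% | 99.9% | 99.9% |
| Age slope −0.2/year | 5.5% | 82.4% | 85.5% | 86.7% |
| Gender difference 4 mmHg | 4.6% | 77.5% | 78.9% | 79.4% |

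Fitting the unstructured three-visit covariance gives 4.3%, 5.0% and 4.2% uncentred, against 100%, 84.0% and 82.5% centred. The DBP version (assumed baseline 88, SD 8; change SD 8; slopes −0.3 and −0.13/year; gender 2.7 mmHg) gives 5.2%, 4.8% and 4.9% against 99.6%, 81.3% and 81.0%. With no true effects the uncentred test rejects in 4.7 to 5.0%, so its size is correct and what it loses is power.

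**Interactions.** With one true interaction at a time, of assumed size, Age×Gender was detected in 4.9% uncentred against 83.2% centred, and Age×SBP in 5.7% against 70.3%. With an assumed Age×SBP coefficient of 0.025 the figures were 7.0% and 86.1%.

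**Range.** Over 36 scenarios (mean age 55 to 65, mean SBP 142 to 150, correlation 0.3 or 0.7, n 180 or 215), main-effect detection was 3.5 to 7.0% uncentred. Centred, it was 95.6 to 100% (SBP), 61.5 to 97.1% (age) and 65.1 to 91.0% (gender). A separate set (age slope 0.15/year, BMI slope −0.4) with narrow spreads (age SD 8, BMI SD 3, SBP SD 7) and correlation 0.7 brought centred detection down to about 35% for age and 34% for BMI, with uncentred still about 4%.

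**What does not change.** Centring leaves the fitted values, the visit test and the four-way test the same. Sequential tests in the written order are the same on either scale, because every lower-order term precedes the products that contain it.

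**The case against.** The strongest reply is that the problem is conditional twice over. The SAP does not name partial tests, and silence on centring is not a decision to use uncentred values. The template code cannot settle it: it is schematic, with no patient subject or covariance type shown. The table shells, which fix the output, are not among the documents. A reader might infer that the SAP prescribes Type 3 tests on uncentred values; it does not. What stands is that a real age effect could be detected in about 5% or about 85% of trials depending on a choice the plan leaves open.

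A second reply is that the detection rates assume purely additive effects of chosen sizes. That is fair. If true interactions exist, the uncentred main-effect test answers an extrapolated question and may err either way, so it would be too strong to say that it always misses real effects. Nor would a non-significant row show that a covariate does not matter.

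Third, this is a supplementary table. Protocol 12.5 does not plan it, and it has no decision rule and no treatment contrast. That stands and sets the severity.

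**Conclusion.** The point holds conditionally and is minor. If the tests are partial and the covariates uncentred, all four main effects and nine of the ten two- and three-way interactions are tested at covariate values that cannot occur. In the settings examined, detection then stays near 5%, against about 70 to 100% centred in the base case and as low as about a third when covariates vary little. The inflation of the standard errors follows from algebra. The detection rates rest on assumed distributions and effects, since only n and the SD come from the documents.

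A reader might infer that the trial's efficacy conclusion is at risk. It is not: the primary paired t-test, its per-protocol and all-patient sensitivity analyses, the secondary paired t-tests and the model fit are untouched. The effect is confined to the covariate tables from 16.1.4 and the added MMRMs in 16.2.1.1 to 16.2.1.3.

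**What to change.** State in SAP 16.1.4, and for the MMRMs in 16.2.1.1 to 16.2.1.3, that age, BMI and baseline SBP or DBP are centred at the analysis-set mean before the products are formed, and name the test type (for example Type 3). Taking the main effects from a model without interactions is not sufficient alone, because the interaction p-values need centred covariates too.

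The cost is one or two sentences and a line of code, with no new data. SAP section 4 requires an amendment if a table shell changes. Centred main effects describe the average patient, not every patient. Part of any baseline-SBP slope will still be regression to the mean, given the BP entry threshold and single arm, so the age and gender rows gain most.

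Housekeeping only: align the template code with 16.1.4 (patient as subject, unstructured type, sex versus Gender), delete the repeated four-way term, and repair the two broken cross-references.
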